**Instructions:**

The following information in the format provided below is an application for Dartmouth-Hitchcock Health review. Read through each section and **respond to each item (even if to indicate NA - not applicable)**. Please also review the CHECKLIST for Full Committee Submission. We have provided some guidance information under each question.

Please define all acronyms at first use and attach a glossary if more than 3 acronyms are used in this application.

When revising a D-HH reviewed Study Plan for further review, please track the changes. To turn on tracking in this document in Microsoft Word:

- 1) Display the forms and reviewing toolbars.
- 2) Unlock the form by clicking on the lock icon on the forms toolbar.
- 3) Turn on change tracking by clicking the icon on the reviewing toolbar.
- 4) Lock the form by clicking again on the lock icon on the forms toolbar.

**Attachments:**

Complete and submit Attachment(s) if applicable to the research study.

Attachments may be downloaded from this webpage: <http://www.dartmouth.edu/~cphs/tosubmit/forms/StudyPlanAttach>

Attachment A: Nonsignificant Risk Devices  
 Attachment B: Placebo  
 Attachment C: Genetic Research  
 Attachment D: Employees and Students  
 Attachment E: Illiterate Participants  
 Attachment F: Research Involving Children  
 Attachment G: Research Involving Individuals With Impaired Decision-Making Capacity  
(formerly referred to as incompetent)  
 Attachment H: Request for Waiver of Participant Consent  
 Attachment I: Request for Waiver of Participant Signed Consent Form  
 Attachment J: Drugs or Biologics  
 Attachment L: International Research  
 Attachment M: Pregnant Women, Fetuses and Neonates

---

**Local Principal Investigator:** **[name]**

**Department:** **Neurology**

**Study Title:** **Microelectrodes in Epilepsy**

**Funding Source (Sponsor):** **Department of Neurology Funds**

**D-HH Study Plan Version Date:** **30Mar2020**

**1. Abstract.**

Provide an abstract of the proposed research **in language that can be understood by a non-scientist**. The abstract should summarize the objectives of this project and the procedures to be used, with an emphasis on what will happen to the subjects. **(Maximum 250 words)**

The standard-of-care for medically refractory epilepsy is resective brain surgery. In certain patients, precise localization of the epileptic focus is done using intracranial EEG (iEEG) recording. In this type of EEG recording, electrodes are placed on the brain surface or inserted into the brain through an opening in the skull. In addition to standard electrode recording, several epilepsy centers have independently developed ultra thin microelectrode technology. Microelectrodes are only several micrometers thick and are uniquely useful because they are able to record the activity of single neurons in isolation. Such recording has tremendous clinical potential in epilepsy surgery and tremendous research potential in cognitive neuroscience. This IRB study plan outlines our clinical and research interests in the use of FDA approved, commercially available, dual macro-micro electrode system in patients who require intracranial EEG recording prior to epilepsy surgery.

## **2. Objectives & Hypotheses:**

List your research objectives and hypotheses.

We have two fundamental objectives and hypotheses. Our first objective is to investigate the usefulness of microelectrode technology in epilepsy surgery. We hypothesize that microelectrode recording will provide unique and novel information on the specific epileptic potential of the implanted brain tissue. Our long-term aim is to improve our paradigms for epilepsy surgery. Our second objective is to investigate the activity of single neurons during specific cognitive tasks. We hypothesize that such analysis will help to predict possible cognitive deficits of epilepsy surgery and provide unique insight into the fundamental mechanisms of cognition and behavior.

## **3. Introduction:**

a) Explain the background of this project so that we will understand why it is important to perform this research project. b) Summarize previously published data and pilot studies. Be sure to include a discussion of any data that do not support the study hypothesis. If a study similar to the one being proposed has already been completed, explain why the proposed study is necessary. c) For studies designed to compare or evaluate therapies, there should be a statement of the relative advantages or disadvantages of alternative modes of therapy. d) If not obvious, explain why human subjects are necessary. Include references for all published data cited. If a formal protocol for the study exists, page references to the protocol are acceptable.

Patients who have recurrent unprovoked seizures despite adequate treatment with antiepileptic medications have medically refractory epilepsy (1). This condition affects approximately 30% of all patients diagnosed with focal epilepsy in the United States. The standard of care for this group of patients is referral for epilepsy surgery. Epilepsy surgery has been well demonstrated to be an effective treatment option for these patients with high seizure freedom rates and low morbidity in properly selected patients (2). Each patient referred for epilepsy surgery undergoes a pre-surgical evaluation with a goal of precise localization of the epileptogenic region and determining the probable cognitive and functional morbidity for the surgery. The pre-surgical evaluation frequently requires the recording of seizures using intracranial EEG (iEEG). In this technique, specially designed electrodes are surgically implanted into target regions of the patient's brain by a trained neurosurgeon and epileptiform activity is recorded. IEEG recording has a long track record of being an effective method of seizure localization (3) with a complication rate of 2-4% (4,5). This method has been used successfully at the DHMC

Epilepsy Center on hundreds of patients since 1992. The recording of iEEG for conventional clinical applications is done using a standard macroelectrode system. A macroelectrode is either a soft plastic strip with multiple 5 mm disc electrodes or a rigid 10 cm needle electrode with multiple contacts along its length. Macroelectrodes are designed to record the summated activity of relatively large groups of neurons located in the vicinity of the electrode contact. Although macroelectrode iEEG recording is the mainstay of surgical epilepsy with established clinical indications, significant limitations are known.

Currently, several well-established epilepsy centers in the United States (for instance, UCLA and Mayo Clinic) are investigating the use of microelectrode systems in epilepsy surgery to supplement the standard macroelectrode recording. Microelectrodes are ultra thin filament electrodes with tip diameters of 3 to 10 micrometers which are able to record the activity of small groups or even single neurons, i.e. single unit potential recording. Supplementary microelectrode recordings are obtained using commercially available, FDA-approved, dual macro-micro electrode systems. These dual systems do not require the insertion of separate and additional microelectrode catheters but use the standard iEEG electrode to deliver the microelectrodes to the target brain regions. The major benefit of this novel design is that the rate of complications from such dual electrode systems is the same and for the standard iEEG electrodes.

The primary aim of supplementing standard iEEG recording with single unit recording is to obtain additional information about the epileptogenic potential of the brain region that is implanted. Initial research in this area was done in the 1980's at UCLA Medical Center where microelectrode recordings of epileptogenic brain tissue showed anomalous bursting patterns, coupled neuronal firing, and increased local inhibition (6, 7). At the same center in the 1990's high frequency oscillations called fast ripples were recorded in patients undergoing pre-surgical evaluation (8, 9) and Braquin et al Annals of Neurology 2002). Fast ripples are ultra-fast neuronal oscillations in the 80 to 1000 Hz range which have been proposed to be the exclusive signatures of epileptogenic cortex (10). Most recently, dual macro-micro system to record fast ripples and determined that they frequently appeared in the microelectrode recording and were not apparent in the standard macroelectrode recording (11). These findings suggest that fast ripples are generated by microscopic neuronal structures which are frequently too small to be recorded using the standard macroelectrode system. Therefore, single unit recording may offer clinically relevant information for epilepsy surgery.

A second yet no less important aim of recording single unit potentials is to gain better understanding of the role of the epileptogenic cortex in cognitive function. Once localization of epileptogenic cortex is established, the functional role of this cortex and possible cognitive deficits following resection must be established. Present paradigms require assessment of cognitive function during the electrical stimulation of macroelectrode contacts which can establish the eloquence of the underlying cortex. Recording of single unit potentials with microelectrodes during specifically designed neuropsychological tasks may offer unique insight into the function of epileptogenic cortex. For example, studies done at UCLA Medical Center have shown that the recording of single unit potentials during specific memory tasks has provided relevant information regarding the functional state of the hippocampus (12). Therefore, recording of single unit potential during specific cognitive tasks may provide important information on the functional integrity of the region of the brain where resection is planned.

A third aim of recording single unit potentials is to investigate the activity of single neurons during specific cognitive tasks. For instance, single unit recording from the hippocampus using the dual macro-micro electrode system during specific cognitive tasks has generated a novel insight into the organization of the human semantic memory system (13). Currently, patients at DHMC undergoing iEEG recording

may have depth electrodes in the orbitofrontal region, the insula, the amygdala, and the hippocampus. Investigation of single unit activity in these patients during performance of specific tasks may generate unique and novel insight into the function of these brain regions in behavior. For instance, investigation of the role of mirror neurons in social behavior may be done by recording the activity of insular neurons during observation of facial expression. Furthermore, single unit activity in the orbitofrontal region during Go-No Go tasks may offer novel insight into the role of this brain region in impulse control.

In summary, we have two concurrent goals for the use of microelectrode recording in patients undergoing iEEG for surgical treatment of medically refractory epilepsy. Our most salient goal is to augment the standard iEEG recording with additional microelectrode recording which may help to identify regions of epileptogenic cortex. Our second goal is to augment our ability to predict the cognitive risk of epilepsy surgery and investigate the role of the specific brain region in cognition and behavior. For these goals, we will utilize a safe, commercially available, FDA approved dual micro-macro electrode system. Our hypothesis is that such recording will elucidate specific characteristics of brain regions with epileptogenic potential, will offer novel insights into cognitive neuroscience, and help to predict neuropsychological outcomes of surgery.

#### **4.Design, procedures, materials and methods:**

Use a level of detail similar to what would be used when submitting an article for publication in a peer reviewed journal. Explain the study procedures, data collection, and analysis process. Please define terms and explain concepts which might be confusing to reviewers who are not expert in the area of the study. If a formal protocol for the study exists, page references to the protocol are acceptable.

Patient selection. Patients with medically refractory epilepsy are referred to DHMC for surgical evaluation. The first stage of the evaluation includes inpatient video EEG monitoring, epilepsy protocol MRI, and a neuropsychological evaluation. Following the initial evaluation, each patient's case is discussed in the epilepsy surgery conference. The conference is attended by all Dartmouth epilepsy neurologists and neurosurgeons. A consensus among all physicians is reached regarding further evaluation. Approximately 50% of patients require intracranial EEG (iEEG) recording prior to epilepsy surgery. If a patient requires iEEG, the strategy for the exact type of electrode implantation is determined at the same surgical conference. Subsequently, the need for iEEG monitoring is discussed with the patient in the outpatient clinic. Patients who meet clinical indication for iEEG recording will be asked to participate in the research study. If the patient agrees, certain standard electrodes will be substituted with the dual micro-macro electrodes during the iEEG recording.

Electrodes. Ad-tech is the largest manufacturer and supplier of intracranial electrodes for use in epilepsy surgery. Ad-tech standard macroelectrodes have been used at Dartmouth-Hitchcock Medical Center since 1992 in hundreds of iEEG cases. In addition to macroelectrodes, Ad-tech currently manufactures two types of dual macro-micro electrode systems that will be used in the study. The appropriate type of electrode system will be determined by the study team.

One system is designed to mimic the original macroelectrode design with the addition of ultra-thin microelectrodes. The original macroelectrode dimensions and properties are retained and additional microelectrodes are positioned at the tip. Leads for the macro and micro electrode recording are separate and are connected to two distinct recording systems. Safety information for the use of the dual electrodes is provided from a single retrospective study of 24 patients who underwent the dual electrode implantation at Mayo Clinic. The complication rate for microelectrodes was 4% compared to 6% for standard electrode systems. Attachment #1 and Attachment #2 address the safety of the electrodes.

The second system (Behnke Fried/Micro Inner Wire Bundle) consists of an outer macro contact depth electrode that accepts delivery of an inner micro wire bundle. The micro contacts extend past the tip of the macro depth electrode.

Data Recording. Recording of iEEG using macroelectrodes has been routinely performed at Dartmouth using the Natus system. Recording of microelectrode potentials will be done using a separate Digital Lynx system or the clinical Natus system. The two systems are distinct and will not share information. The Digital Lynx system is a state-of-the-art microelectrode recording system manufactured by Neuralynx. Neuralynx provides the highest quality microelectrode recording equipment. The Digital Lynx system is not FDA approved for clinical use. However, it has been fully tested and meets the 60601 medical safety standards, has the 60601-1 safety certification for medical devices, and has meets the 60601-2-26 safety standards for EEG equipment. This system is available for clinical use through the lab of [name]. Attachment #3 addresses the safety of the Digital Lynx System.

**Cognitive Tasks.** Patients who agree to participate in microelectrode studies may be asked to participate in a study which involves a cognitive task. Each task will be specifically designed to elicit a specific cognitive function important to testing of the regions where electrodes are implanted. The task could be a memory task, such as remembering of word pairs if electrodes reside in the hippocampus. The task may involve perception of facial emotion, mimicry of facial movements, mimicry of planned movements, smell appreciation, taste appreciation, appreciation of disgust, or visual spatial analysis. The type of task that a patient gets will depend on the region of the brain that is implanted by the microelectrode.

**Data Analysis.** Data on neuronal discharge characteristics will be recorded using the 64 Chanel Digital Lynx system running Cheetah software. The characteristics of fast ripples, and the data on neuronal firing characteristics during specific cognitive tasks will be exported to Matlab software for statistical analysis. Data analysis will be done by either the study team at DHMC/Dartmouth College, or by collaborators at Columbia University.

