4. IQ>70
5. medically refractory focal epilepsy requiring intracranial EEG for pre-surgical evaluation deemed medically necessary
6. no contraindications to intracranial electrode study
7. able and willing to participate in research

Exclusion criteria:

1. does not meet the inclusion criteria

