**7. Statistical Methods and Review Statement:**

**a)** Specify the primary endpoint, as well as other endpoint(s).

The primary hypothesis is that high oscillations (fast ripples) occur in epileptogenic cortex and are absent in non-epileptogenic cortex. Our secondary hypothesis is that single unit activity recorded from various electrode positions in the brain will correlate with specific cognitive tasks.

**b)** State the statistical analysis plan, including all hypothesis tests (e.g., t-test, chi-square), and estimation methods related to the primary endpoint. If a formal protocol for the study exists, page references to the protocol are acceptable.

The recording of high frequency oscillations will require only basic statistical analysis using chi-square testing. The analysis of neuronal discharge characteristics and temporal association with specific cognitive tasks will be done using Matlab.

**c)** Justify the sample size, using the concepts of power, type I error, and effect size if applicable. If a formal protocol for the study exists, page references to the protocol are acceptable.

We are planning to enroll up to 50 patients over an extended period of time. The power calculations and effect size, will depend on the cognitive task applied in the individual patient for the specific electrode array.

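### No rule links the electrodes chosen for substitution to tissue class, so the fast-ripple comparison may have few control sites and be confounded by patient and, in part, by brain region

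*Combined protocol and SAP*

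**What the plan says.** Section 7, item a, sets a two-class comparison: "The primary hypothesis is that high oscillations (fast ripples) occur in epileptogenic cortex and are absent in non-epileptogenic cortex". Item b gives the analysis in one sentence: "The recording of high frequency oscillations will require only basic statistical analysis using chi-square testing". It states no unit of analysis, pairing or stratification. Item c gives the size, "We are planning to enroll up to 50 patients over an extended period of time", and then leaves power to the other objective: "The power calculations and effect size, will depend on the cognitive task applied in the individual patient for the specific electrode array".

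Under Patient selection in section 4, the surgical conference fixes the implantation strategy on clinical grounds. Then: "If the patient agrees, certain standard electrodes will be substituted with the dual micro-macro electrodes during the iEEG recording". Under Electrodes, the study team chooses the type of dual system; nothing is said about its site.

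In section 5, the criterion closest to this point is "medically refractory focal epilepsy requiring intracranial EEG for pre-surgical evaluation deemed medically necessary". The other inclusion criteria cover age, sex, handedness, IQ, absence of contraindications, and ability and willingness. The only exclusion is failure to meet these. None concerns which tissue will be sampled. The Introduction (section 3) says that patients may have depth electrodes in four named regions, so control sites are possible but not required.

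**The concern.** The hypothesis can be tested only if microelectrodes record from both tissue classes. Intracranial recording is done to localize the epileptogenic region (section 3), so the clinical plan may lean towards suspected foci. Substitution then takes an unspecified subset of that plan. Three consequences follow.

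- Control sites may be few. Half of the hypothesis is a claim of absence, so the number of control sites limits what can be concluded.
- The two classes may come largely from different patients. An ordinary chi-square over sites would then mix tissue class with patient.
- The two classes may come from different structures, for example hippocampus against insula. Tissue class would then also be mixed with region.

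The gap would be hard to repair late. Section 12 expects 2-3 patients a year and section 16 expects 5-8, so 50 patients would take from 50/8, about 6 years, to 50/2, or 25 years.

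**Working it through.** **The plan's own figure.** The only figure is the ceiling of 50 patients (section 7c). It cannot be reproduced: no type I error, power, fast-ripple rates, sites per patient or class split is given. What follows is illustration. The assumed values are k dual electrodes per patient (each counted as one site), a share p of sites in epileptogenic cortex, and independent sites. None of these is in the documents.

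**Step 1. Patients supplying both classes.** P(both) = 1 − p^k − (1 − p)^k.

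| p | k = 1 | k = 2 | k = 3 |
|---|---|---|---|
| 0.8 | 0 | 1 − 0.64 − 0.04 = 0.32 (16 of 50) | 1 − 0.512 − 0.008 = 0.48 (24 of 50) |
| 0.7 | 0 | 1 − 0.49 − 0.09 = 0.42 (21 of 50) | 1 − 0.343 − 0.027 = 0.63 (31.5 of 50) |
| 0.5 | 0 | 1 − 0.25 − 0.25 = 0.50 (25 of 50) | 1 − 0.125 − 0.125 = 0.75 (37.5 of 50) |

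The k = 1 column needs no assumption about p: one site cannot supply two classes.

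**Step 2. Control sites in the whole cohort.** Expected number = 50 × k × (1 − p). With k = 1 this is 10 (p = 0.8) to 15 (p = 0.7); with k = 2 it is 20 to 30. The chance of no control site at all with k = 1 is p^50: 0.8^50 = 0.000014, about 0.001%. Even at p = 0.95 it is 0.95^50 = 7.7%.

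**Step 3. What few control sites can show.** If no fast ripples are seen in m control sites, the one-sided 95% upper bound on the control rate is 1 − 0.05^(1/m). This gives 45% for m = 5, 26% for m = 10, 11% for m = 25 and 5.8% for m = 50.

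**Step 4. Power under imbalance.** Assume 50 sites in total, fast-ripple rates of 60% and 20%, and two-sided 5%. Power = Φ[(d − 1.96 × SE0)/SE1], with d = 0.4, SE0 the pooled and SE1 the unpooled standard error. With 40 epileptogenic and 10 control sites, the pooled rate is (24 + 2)/50 = 0.52. Then SE0 = √(0.52 × 0.48 × (1/40 + 1/10)) = 0.1766, SE1 = √(0.24/40 + 0.16/10) = 0.1483, and power = Φ(0.363) = 64%. In the same way, 25 control sites give 84.5%, 15 give 77% and 5 give 38%.

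Steps 3 and 4 treat sites as independent. Steps 1 and 2 also ignore any tendency of one patient's sites to fall in the same class.

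**The case against.** A reader might infer that the trial could finish with no control cortex at all. The documents do not support that. On assumptions unfavourable to the plan, step 2 gives 10 to 15 control sites with a single dual electrode each. Complete absence would need substitution to be confined to the suspected focus, and no section says so. A reader might also picture a typical participant with dual electrodes only in a suspected hippocampus. No section describes typical substitution, and section 3 foresees implants in several regions.

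The Cognitive Tasks paragraph might be read as showing that sites are picked to suit tasks. It says the reverse: "The type of task that a patient gets will depend on the region of the brain that is implanted by the microelectrode". The task follows the site.

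It is also fair to say that counting patients with both classes measures a within-patient design that the plan never adopts, and that 70-80% is a narrow, unfavourable range. Both points stand, which is why the 50% row is shown and the figures are called illustrations. Neither removes the gap: with no pairing stated, nothing guards against tissue class following the patient.

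Two further objections stand in part. A rule based on suspected onset before implantation does not fix a site's true class, which the documents never define. And a within-patient contrast removes differences between patients but not between regions.

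**Conclusion.** The concern holds in limited form. The plan has no rule connecting substitution to tissue class, and its chi-square test has no stated pairing. The primary comparison can therefore be short of control sites and confounded by patient and, in part, by region. This rests on reading the sections together and on no assumed number.

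The size is uncertain. The range of 32-63% of patients supplying both classes assumes two or three dual electrodes and 70-80% of independent sites in epileptogenic cortex. At 50% it becomes 50-75%. The plan should be changed, because a better design is available within the existing clinical implant plan. The study is not unworkable without the change, and cohort-wide absence of control tissue is not a realistic prediction. Eligibility needs no amendment: the missing rule belongs in sections 4 and 7.

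**What to change.** **Section 4.** State that where two or more electrodes are to be substituted, and the clinical implant plan already covers both areas, the dual electrodes are chosen from that plan. At least one should lie in the suspected onset region and at least one outside it, subject to the surgical conference's agreement. No electrode is added or moved for research. Record the expected class of each site before implantation. Assign the final class from the clinical macroelectrode evaluation, without reference to the fast-ripple results.

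**Section 7.** Name a within-patient contrast, matched or stratified by patient, as primary in place of the chi-square test. Tabulate brain region by tissue class, so that remaining confounding by region is visible. Report patients with one class in a supportive pooled analysis and do not discard them.

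**Cost.** The change is mainly protocol wording and record-keeping, with less freedom in choosing sites. Some micro contacts would lie outside the suspected onset region for research reasons. Attachment G puts implant risk no higher than for standard electrodes, while section 13 calls overall risk minimally greater and names a theoretical neuronal injury, so the conference should weigh this. Patients with one class, including all those with a single substitution, would not inform the primary estimate. At the stated accrual that loss is real.

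### Two dual electrode systems and two recorders are allowed with no rule for choosing between them, and the primary chi-square has no term for either; if the instruments differ and their mix differs by tissue, the comparison is biased

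*Combined protocol and SAP*

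**What the plan says.** Section 4 (Electrodes) names "two types of dual macro-micro electrode systems that will be used in the study" and then states: "The appropriate type of electrode system will be determined by the study team". It gives no criterion and does not say whether the choice is made once per patient or separately for each electrode.

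The two systems are described differently. For the first, "The original macroelectrode dimensions and properties are retained and additional microelectrodes are positioned at the tip". For the second, a micro wire bundle inside a depth electrode, "The micro contacts extend past the tip of the macro depth electrode".

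Section 4 (Patient selection) sets the order of events. For a patient who needs intracranial EEG, "the strategy for the exact type of electrode implantation is determined at the same surgical conference"; after consent, "certain standard electrodes will be substituted with the dual micro-macro electrodes during the iEEG recording".

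Section 4 (Data Recording) allows micro signals on the Digital Lynx or on the clinical Natus system, with no rule for which. The Data Analysis paragraph names only the Digital Lynx, for neuronal discharge data.

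Section 7a states the primary hypothesis: fast ripples occur in epileptogenic cortex and not in non-epileptogenic cortex. Section 7b gives the whole analysis: "The recording of high frequency oscillations will require only basic statistical analysis using chi-square testing". No section mentions stratifying by, adjusting for, or reporting by electrode type or recorder.

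**The concern.** The primary measure is whether a very local signal is picked up. The Introduction (section 3) says that fast ripples often appear on micro contacts and not on macro contacts, and infers that their generators are often too small for a macroelectrode. On that reasoning, detection depends on the recording contact. Where two micro systems with differently placed contacts are in use, the system is a candidate source of variation in the primary measure, and so is the recorder.

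The implantation plan is settled before standard electrodes are substituted, so the suspected focus is known when the type is chosen. Nothing in the plan keeps the type unrelated to the tissue label. If the more sensitive instrument sat more often in epileptogenic sites, fast ripples would look more frequent there with no tissue effect. The opposite mix would mask a real one.

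Accrual is slow. Section 12 expects 2 to 3 patients per year and section 16f expects 5 to 8. Reaching 50 would take from 50/8, about 6 years, to 50/2 = 25 years. The instrument mix may drift over such a period, and a type that was not logged for each contact may be hard to recover later.

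**Working it through.** **The plan's own figure.** Section 7c gives up to 50 patients, with no alpha, power, effect size or detection rates. It cannot be reproduced, and no corrected sample size can be derived. What follows is an illustration on assumed rates.

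**Set-up.** There is no true tissue difference. Detection is p_H with the more sensitive type and p_L with the other, in both tissues. The more sensitive type makes up a share s_E of epileptogenic sites and s_N of non-epileptogenic sites. Sites are independent, with n per tissue, and the test is a two-sided 5% Pearson chi-square. The documents give none of p_H, p_L, s_E, s_N, n or alpha.

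**Apparent difference.** Each apparent rate is s × p_H + (1 − s) × p_L, so the spurious difference is

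Δ = (s_E − s_N) × (p_H − p_L).

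Because this is a product, it is zero if either the mixes or the sensitivities are equal. Both conditions are needed.

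**False-positive rate.** With mean rate p̄ and z = Δ / √(2 p̄(1 − p̄)/n), the rejection rate is about Φ(z − 1.96) + Φ(−z − 1.96).

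For 40% versus 15% detection, a 70/30 mix and n = 40:
- epileptogenic: 0.7 × 0.40 + 0.3 × 0.15 = 0.325
- non-epileptogenic: 0.3 × 0.40 + 0.7 × 0.15 = 0.225
- Δ = 0.4 × 0.25 = 0.10 and p̄ = 0.275
- z = 0.10 / √(2 × 0.275 × 0.725 / 40) = 0.10 / 0.0998 = 1.00
- rejection = Φ(−0.96) + Φ(−2.96), about 17%

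| Detection by type | Mix in the two tissues | n per tissue | Apparent rates | z | Formula | Simulation |
|---|---|---|---|---|---|---|
| equal | 70/30 | 40 | equal | 0 | 5% | 5.2% |
| 40% v 15% | 50/50 | 40 | 27.5% v 27.5% | 0 | 5% | about 4% (exact calculation) |
| 40% v 30% | 70/30 | 40 | 37% v 33% | 0.38 | 7% | 6.2% |
| 40% v 15% | 60/40 | 40 | 30% v 25% | 0.50 | 8% | 7.6% |
| 40% v 15% | 70/30 | 40 | 32.5% v 22.5% | 1.00 | 17% | 15.7–16.5% |
| 40% v 15% | 70/30 | 100 | 32.5% v 22.5% | 1.58 | 35% | 34.8–35.1% |

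The exact figure for the balanced mix holds the number of sites per type fixed. The last two rows differ only in n: more sites make the error worse.

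**Other assumed gaps.** With 50 sites per tissue and a 70/30 mix, 30% versus 50% detection gives 13.1% and 20% versus 60% gives 37.3%.

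**Stratifying by type.** A Cochran-Mantel-Haenszel test stratified by electrode type brings the rate back to about 5% in these scenarios, but it still treats sites as independent. In an assumed example with 25 patients, 4 sites each and no true effect, it rejected 7.2% and 10.9% of the time with a patient random-effect SD of 1 and 2, against 4.8% with none. Stratification alone is therefore not a full remedy.

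**The case against.** The strongest reply is that the plan shows neither ingredient of the bias.

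- **Pooling.** A reader might infer that the two types will be merged in one table. That is the natural default reading of section 7b, but it is not written. The section names no unit of analysis, table layout or handling of devices.
- **Sensitivity.** A reader might infer that one system detects fast ripples better. Nothing in the documents compares the two micro systems. The Introduction contrasts micro with macro contacts, which does not show that contacts at the tip differ from contacts past it.
- **Allocation.** A reader might infer that type follows the suspected focus. No section says so. Choosing the appropriate type is compatible with technical suitability or with one type per patient. The substitution sentence says that some electrodes become dual, not which dual type goes where. With one type per patient and both tissues sampled in equal proportion, the mix is balanced and type does not inflate the test (3.2% to 5.4% in balanced simulations).

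All three points stand, so the concern is conditional. They do not show that the analysis is protected. Equal sensitivity is no better documented than unequal sensitivity, no rule keeps the mix balanced, and the plan does not require the record that would let anyone check either.

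**Conclusion.** The point holds as a conditional gap and a cheap improvement. The plan allows two differently described electrode systems and two recorders, states no rule for choosing between them, and specifies a primary test that takes no account of either. Whether this biases the result depends on two unknowns: a detection gap between instruments, and a difference in their mix between tissues. On assumed values with 40 independent sites per tissue, false positives run from about 5% or slightly less, through 6 to 8%, to 16 to 17%; the last case reaches about 35% with 100 sites per tissue. The bias can go in either direction. The documents do not support saying that the planned comparison is confounded, only that the plan neither prevents confounding by instrument nor would detect it.

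**What to change.** In section 4, require electrode type and recorder to be logged for every micro contact, and reconcile the Data Recording paragraph (two recorders) with the Data Analysis paragraph (one recorder named).

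In section 7b, replace the unadjusted chi-square with a comparison of fast-ripple detection by tissue label that adjusts for electrode type, and for recorder where both are used, and accounts for several sites per patient. One example is a logistic model with electrode type and a patient random effect or cluster-robust errors. Because the hypothesis is that fast ripples are absent in one tissue, name a fallback for an empty cell, such as a penalised fit. Report detection by type, and the cross-tabulation of type by tissue label: if a type occurs under only one label, adjustment cannot separate the two and the report should say so.

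The cost is two logged variables, somewhat more analysis work, and some loss of precision if one type is rarely used. No electrode or procedure is added. The change should not prescribe which type is implanted at which site; recording the type and analysing by it is enough.
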